15.2 Adverse Events

All adverse events analyses will be based on the safety population.

An AE is any untoward medical occurrence in a subject or clinical investigation subject administered a pharmaceutical product, which does not necessarily have a causal relationship with the treatment. An AE can therefore be any unfavorable and unintended sign (including a laboratory finding), symptom or disease temporally associated with the use of an IMP, whether considered related to the IMP or not. All AEs will be coded using the most recent Medical Dictionary for Regulatory Activities MedDRA version, Version 20.1 or later.

A treatment emergent adverse event (TEAE) is defined as an AE that begins or worsens after at least one dose of the IMP has been administered. AEs that started before administration of IMP or more than 30 days after last dose of IMP will not be considered TEAEs.

Every AE listing will include the following information:

- System organ class (SOC) and preferred term (PT)
- Start and end date/time
- Days under treatment
- Duration
- Seriousness criteria
- Relationship with M8891
- Common Terminology Criteria for Adverse Events (CTCAE) toxicity grade
- Other causality factors
- Action taken with M8891
- Other actions taken
- Outcome
- Whether AE is dose-limiting toxicity

There will be a listing of all AEs, sorted by SOC and PT.

The following summaries will be presented by dose group and overall using the safety population:

- Number of subjects with the following kinds of TEAEs:
 - Any TEAE
 - Related TEAEs
 - TEAEs leading to withdrawal of trial drug
 - o TEAEs leading to death (overall and by reason for death)
 - Serious TEAEs
 - o Related serious TEAEs
 - TEAEs with CTCAE grade ≥ 3
 - o Related TEAEs with CTCAE grade ≥ 3
 - TEAEs leading to dose reduction
 - o TEAEs leading to temporary interruptions of trial drug
- TEAEs by SOC and PT
- Serious TEAEs by SOC and PT
- TEAEs leading to withdrawal of trial drug, dose reduction, temporary interruptions of trial drug, and death
- Non-serious TEAEs occurring with incidence in PT greater than 5% in at least one dose group, by SOC and PT

AEs will be summarized by worst severity per subject, using the MedDRA PT as event category and MedDRA primary SOC as Body System category.

In general, each subject will be counted only once within each PT or SOC. If a subject experiences more than one AE within a PT or SOC, only the AE with the strongest relationship or the worst severity, as appropriate, will be included in the summaries of relationship and severity.

AEs with missing classifications regarding relationship to study treatment and start date greater or equal to start of study treatment will be considered as related to study treatment.

Incomplete AE-related dates will be handled as follows:

- In case the onset date is missing completely or missing partially but the onset month and year, or the onset year are equal to the start of trial treatment then the onset date will be replaced by the minimum of start of trial treatment and AE resolution date.
- In all other cases, the missing onset day or missing onset month will be replaced by 1.
- Incomplete stop dates will be replaced by the last day of the month (if day is missing only), if not resulting in a date later than the date of subject's death. In the latter case, the date of death will be used to complete the stop date.

- In all other cases, the incomplete stop date will not be imputed. If the stop date of an AE is after date of cutoff, outcome of AE is ongoing at cutoff.
- Further information after cutoff (like fatal outcome) might be taken from Safety data base and reported separately.

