4.1.2 Secondary Objectives

Secondary objectives are:

- To evaluate the safety profile and tolerability of M8891 as a single agent
- To investigate the PK profile of M8891 as single agent
- To assess the antitumor activity of M8891 as single agent according to Response Evaluation Criteria in Solid Tumors (RECIST) v1.1
- To determine the recommend Phase II dose (RP2D) as single agent.

CCI

4.2

Part 2, M8891 combined with Cabozantinib, mRCC

In Part 2 of this study, M8891 combined with cabozantinib will be administered in subjects with mRCC.

4.2.1

Part 2A, Dose Escalation

Table 6

Part 2A Objectives and Endpoints

Objectives	Endpoints (Outcome Measures)

Primary
 
To determine the recommended dose for expansion (RDE) (MTD, if reached) of M8891 combined with cabozantinib in subjects with mRCC, based on safety, tolerability, and antitumor activity	
Occurrence of DLTs in subjects with mRCC receiving M8891 combined with cabozantinib during the first 22-day treatment cycle (21 days of M8891 combined with cabozantinib, preceded by 1 day of M8891 alone) based on predefined set of AEs.Occurrence of TEAEs (including TEAEs leading to death or discontinuation of treatment) in subjects with mRCC receiving M8891 combined with cabozantinib. Any AEs that occur or worsen between start of study intervention and 30 days after end of study intervention will be considered TEAEs.Study clinically relevant abnormal changes in clinical laboratory measures from baseline, vital signs, ECOG performance status, and ECGs from start of study intervention to 30 days after end of study interventionObjective response according to RECIST v1.1 as assessed by Investigators

Objectives	Endpoints (Outcome Measures)

Secondary
 
• To characterize the PK profile of M8891 (single and multiple dose exposure) combined with cabozantinib in subjects with mRCC• To further assess antitumor activity of M8891 combined with cabozantinib in subjects with mRCC	
• PK parameters of M8891 in terms of C_{max}, t_{max}, AUC_{0-t} on Day 1 Cycle 1, (combined with cabozantinib, single dose)• PK parameters of M8891 in terms of C_{max}, t_{max}, AUC_{0-t} on Day 8 and Day 15 Cycle 1, and Day 1 Cycle 2 (combined with cabozantinib, multiple dose)
CC1	

[figure not shown]

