- Is otherwise considered to be medically important. (Note: Important medical events that may not result in death, be life-threatening, or require hospitalization may be considered as SAEs when, based upon appropriate medical judgment, they may jeopardize the subject or may require medical or surgical intervention to prevent one of the outcomes listed above. Examples of such events include allergic bronchospasm requiring intensive treatment in an emergency room or at home, blood dyscrasias or convulsions that do not result in inpatient hospitalization, or the development of drug dependency or drug abuse.)

For the purposes of reporting, any suspected transmission of an infectious agent via an IMP is also considered an SAE, as described in Section 7.4.1.4.

Events that Do Not Meet the Definition of an SAE

Elective hospitalizations to administer, or to simplify trial treatment or trial procedures (for example, an overnight stay to facilitate chemotherapy and related hydration therapy application) are not considered SAEs. However, all events leading to unplanned hospitalizations or unplanned prolongation of an elective hospitalization (for example, undesirable effects of any administered treatment) must be documented and reported as SAEs.

Events Not to Be Considered as AEs/SAEs

Medical conditions present at the initial trial visit that do not worsen in severity or frequency during the trial are defined as Baseline Medical Conditions and are not to be considered AEs.

AE/SAEs Observed in Association with Disease Progression

Progression of the disease/disorder being studied assessed by measurement of lesions on radiographs or other methods as well as associated clinical signs or symptoms (including laboratory abnormalities) should not be reported as an AE/SAE, unless the subject's general condition is more severe than expected for the subject's condition and/or unless the outcome is fatal within the AE reporting period (as defined in Section 7.4.1.3).

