7.4.1.2 Methods of Recording and Assessing Adverse Events

At each trial visit, the subject will be queried on changes in his or her condition. During the reporting period, any unfavorable changes in the subject's condition will be recorded as AEs, whether reported by the subject or observed by the Investigator.

Complete, accurate and consistent data on all AEs experienced for the duration of the reporting period (defined below) will be reported on an ongoing basis in the appropriate section of the eCRF. All SAEs must be additionally documented and reported using the appropriate Report Form as described in Section 7.4.1.4.

It is important that each AE report include a description of the event, its duration (onset and resolution dates (and times when it is important to assess the time of AE onset relative to the recorded treatment administration time), its severity, its causal relationship with the trial treatment, any other potential causal factors, any treatment given or other action taken, including dose modification or discontinuation of the IMP, and its outcome. In addition, serious cases should be identified, and the appropriate seriousness criteria documented. If an AE constitutes a DLT, this must be documented accordingly.

Specific guidance can be found in the eCRF Completion and Monitoring Conventions provided by the Sponsor.

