7.4.1.3 Definition of the Adverse Event Reporting Period

The AE reporting period for safety surveillance begins when the subject is initially included in the trial (date of first signature of first informed consent) and continues until the EOT visit and through the safety follow-up period for SAEs. Subjects with SAEs ongoing at EOT Visit must be followed during the safety follow-up.

Any SAE assessed as related to M8891 must be reported whenever it occurs, irrespective of the time elapsed since the last administration of M8891.

7.4.1.4 Procedure for Reporting Serious Adverse Events, Adverse Events of Special Interest and Dose Limiting Toxicities

Serious Adverse Events

In the event of any new SAE occurring during the reporting period, the Investigator must immediately (within a maximum of 24 HOURS after becoming aware of the event) inform the Sponsor or its designee in writing. All written reports should be transmitted using the SAE Report Form, which must be completed by the Investigator following specific completion instructions.

In exceptional circumstances, an SAE (or follow-up information) may be reported by telephone; in these cases, a written report must be sent immediately thereafter by fax or e-mail. Names, addresses, and telephone and fax numbers for SAE reporting will be included in the trial-specific SAE Report Form.

Relevant pages from the eCRF may be provided in parallel (for example, medical history, concomitant drugs). Additional documents may be provided by the Investigator, if available (for example, laboratory results, hospital report, autopsy report). In all cases, the information provided on the SAE Report Form must be consistent with the data about the event recorded in the eCRF.

The Investigator must respond to any request for follow-up information (for example, additional information, outcome, final evaluation, other records where needed) or to any question the Sponsor/designee may have on the AE within the same timelines as those noted above for initial reports. This is necessary to ensure prompt assessment of the event by the Sponsor or designee and (as applicable) to allow the Sponsor to meet strict regulatory timelines associated with expedited safety reporting obligations.

Requests for follow-up will usually be made via the responsible Monitor, although in exceptional circumstances the Global Drug Safety department may contact the Investigator directly to obtain further information or to discuss the event.

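### SAP 15.2 gives two answers for an AE that starts between consent and first dose and worsens on treatment: one sentence makes it a TEAE, the next excludes it

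*SAP*

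**What the plan says.** SAP Section 15.2 defines a TEAE in two consecutive sentences. The first says that a TEAE "is defined as an AE that begins or worsens after at least one dose of the IMP has been administered". The second says that "AEs that started before administration of IMP or more than 30 days after last dose of IMP will not be considered TEAEs".

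The protocol gives no TEAE definition for Part 1. Its only explicit one is for Part 2A (Synopsis and Table 6): "Any AEs that occur or worsen between start of study intervention and 30 days after end of study intervention will be considered TEAEs". That wording does not exclude AEs with onset before dosing.

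On collection, protocol Section 7.4.1.3 says: "The AE reporting period for safety surveillance begins when the subject is initially included in the trial", and dates this to the "date of first signature of first informed consent". Section 5.1.1 allows up to 28 days of screening before the first M8891 dose, and Table 1 schedules AE assessment at screening. Section 7.4.1.1 says that conditions present at the initial visit "that do not worsen in severity or frequency during the trial are defined as Baseline Medical Conditions" and are not AEs. Section 7.4.1.2 requires unfavorable changes in the subject's condition to be recorded as AEs, each with onset and resolution dates and a severity. It leaves further detail to eCRF conventions that are not part of these documents.

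**The concern.** The words on worsening in the first sentence matter only for events that were already present before dosing. The second sentence removes events by start date and makes no exception for worsening. Applied to the start date on the AE record, it cancels the worsening arm of the definition for every record that opened before dosing.

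Occurrence and severity of TEAEs is a Part 1 secondary endpoint (protocol Section 8.3.1.2; SAP Section 5). An error here can go only one way: on-treatment deterioration is left out and nothing is added. The Grade 3 or higher, related and serious TEAE counts would be exposed along with the overall count, in dose groups that may hold only three subjects.

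**Working it through.** The plan gives no figure to reproduce. The check is whether the two sentences agree for each type of AE record, whether any other text settles a disagreement, and how much one event could move a table row.

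**Step 1. Apply each sentence to each case.**

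| AE record | First sentence | Second sentence |
|---|---|---|
| Onset after first dose and within 30 days of last dose | TEAE | Not excluded |
| Onset before first dose, no worsening | Not a TEAE | Excluded |
| Onset before first dose, worsens on treatment, original start date kept | TEAE | Excluded |
| Worsening entered as a new record with a post-dose start date | TEAE | Not excluded |

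The sentences disagree only in the third row.

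**Step 2. Can the third row occur?** Yes. AEs are collected from consent, and up to 28 days can pass between screening and first dose. A new AE in that window has a pre-dose onset and can worsen later.

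**Step 3. Does other text settle it?** I found none.

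- The AE listing in SAP 15.2 carries a start date, an end date and a toxicity grade. It has no worsening date and no link between records.
- The rule that treats a missing relationship as related also depends on the AE start date.
- The rules for incomplete dates deal with missing onset and stop dates. They do not re-date a known pre-dose onset.
- Protocol 7.4.1.2 does not say whether a rise in grade opens a new record.

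**Step 4. Which outputs are exposed?** If the second sentence is applied to the original start date, third-row events leave these outputs:

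- the TEAE summaries in SAP 15.2: any, related, serious, related serious, Grade 3 or higher, related Grade 3 or higher, and those leading to withdrawal, dose reduction, interruption or death, with the tables by SOC and preferred term;
- the TEAE listings in SAP 15.3.

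They stay in these outputs:

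- the listing of all AEs (15.2);
- the worst-severity summary, if it is built on AEs as it is worded (15.2);
- for laboratory changes, the worst post-baseline grades and grade shifts (15.4);
- for deaths, the listing in 15.3.1, which has no TEAE filter.

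The DLT analysis in 15.1 has its own definition and uses the dose escalation set, so the TEAE flag does not enter it.

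**Step 5. Size for one subject.** Adding or removing one subject in a row changes its incidence by 1/n. Group sizes come from the protocol: cohorts of 3 (5.1.3.1), at least 6 at the MTD/RP2D (5.1.3.4), and 3 to 12 per dose level (8.1.1).

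- n = 3: 1/3 = 33 percentage points
- n = 6: 1/6 = 17 percentage points
- n = 12: 1/12 = 8 percentage points
- All dose levels together, taking the anticipated 36 subjects: 1/36 = 3 percentage points

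These are shifts per affected subject in a given preferred-term or Grade 3 or higher row, where the subject has no other event that counts in that row. The row for any TEAE changes only if the subject has no other TEAE at all.

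**The case against.** The strongest reply is that the problem may never arise. The eCRF conventions may open a new record with a new onset date when an event worsens, and the event then passes both sentences. This stands as a limit: the loss is conditional on the original start date being kept. It does not remove the contradiction, because neither document states that convention.

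A second reply concerns pre-existing conditions. Under protocol 7.4.1.1 a condition present at the initial visit is not an AE unless it worsens, so the natural reading is that the AE is the on-treatment worsening, with an on-treatment onset. This also stands. A reader might infer that worsening of pre-existing anemia, fatigue or nausea is generally lost. The documents do not support that. The clear case is the narrower one of an AE that first arises between consent and first dose.

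A third reply is that other outputs still show many of these events, as set out in the working, and that all analyses are descriptive. That softens the consequence. It does not repair the TEAE tables, which are where the secondary endpoint is reported.

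A reader might also infer that the Part 2 primary endpoints are affected, because Part 2A counts TEAEs among them. This SAP is version 1.0 of April 2018, refers to protocol version 2.0, and covers the monotherapy escalation only. Its Section 6 says it will be amended if combination or expansion parts are added. The point for Part 2 is only that the sentence, if carried over unchanged, would conflict with the Part 2A definition.

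**Conclusion.** The contradiction is real, is confined to one type of record, and is not resolved elsewhere in the documents. For an AE with onset between consent and first dose that worsens on treatment, SAP 15.2 gives opposite answers. If the exclusion is applied to the original start date, the Part 1 TEAE summaries and listings under-count, and only in that direction.

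The size is 8 to 33 percentage points per affected subject in a given row of a dose level of 12 down to 3. This should not be read as an estimate of bias, because the documents do not allow the number of such events to be derived. It would also be too strong to say that every pre-dose AE that worsens is lost from all TEAE tables. That assumes a recording convention that the documents leave open.

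The DLT endpoint and the MTD suggestion from the model do not depend on the TEAE flag. The point should be settled before database lock, because it is a stated rule that can misclassify safety events and it is cheap to correct.

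**What to change.** Replace the exclusion sentence in SAP 15.2 with wording such as: *An AE is not a TEAE if its onset precedes the first IMP administration and it does not worsen between first dose and 30 days after last dose, or if its onset falls later than 30 days after last dose.*

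Add one derivation rule that says how a worsening is recorded and dated: either a new record with its own onset date, or a derivation from grade changes on the existing record. If grade is used, say so, because the baseline-condition rule in protocol 7.4.1.1 refers to frequency as well as severity, and a grade derivation would see only severity.

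Use the same wording when the SAP is amended for Part 2, so that it agrees with protocol Table 6.

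The cost is one sentence and one programming rule, plus a check of the eCRF conventions. If those conventions already open a new record at worsening, no new data are needed and the SAP only has to state it. If they do not, the grade changes must be available in the database for the derivation to work.
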